5.2.1 Benefit Assessment

The main potential benefit for subjects with LHON due to the G11778A *ND4* mutation who receive GS010 IVT is halting, reversal (neuroprotection) or improvement of vision loss due to disease progression (neuroenhancement). Statistical modeling of the vision test results from GS-LHON-CLIN-01 indicate that potential benefit from IVT injection of GS010 may be greater in subjects with relatively shorter vision loss duration and with relatively less vision loss at the time of GS010 IVT injection. The appropriately powered Phase III efficacy studies were required and pending analysis to confirm any potential benefit from IVT injection of GS010.

5.2.2 Risk Assessment

This study is not an interventional study and there are no risks from administration of any IMP or study procedure. The long-term follow-up study will assess the safety of gene therapy IMP GS010 that was administered in the RESCUE and REVERSE studies. The risks associated with gene therapy IMPs are as follows:

Risk of Immune Response: Although the eye is considered to be an immune-privileged site,¹³ an expected risk is potential immune responses to the capsid and transgene. Immune reactions against the newly introduced foreign protein or a T-cell response to the capsid could lower the therapeutic efficacy or cause local inflammation. Immune reactions against adenovirus-associated viral vector serotype 2 (AAV2/2) will be monitored throughout the study. The AAV2/2 used in this study has been studied and employed in other ophthalmologic clinical trials such as type 2 trials and to date no major health concerns, including immunologic or clinical, have been reported.¹⁴

Insertional Mutagenesis: Adeno-associated viruses (AAV) are non-integrative viruses. Studies performed in vivo with mouse liver suggest that AAV vectors integrate into the host genome; however no direct evidence of tumorigenesis due to AAV2/2 integration or other AAV serotypes has been observed in all preclinical studies and clinical trial data accumulated so far. This risk is considered as minimal.

Germ-line Transmission: Based on preclinical and clinical data, the risk of germ-line transmission is low. The probability that a recombination event could occur is very low.

Dissemination: The risk of vector shedding after in vivo gene therapy depends on the route of administration and the vector dose administered. An exhaustive report gathered the bio-distribution and shedding data from pre-clinical and clinical studies obtained for the HADV-5 and AAV2/2 vector.¹⁵ These studies conclude that the more compartments the viral vector has

to pass to reach a certain excretion route, the lower the risk of shedding is, due to either dilution of the viral vector, or degradation in case of passage through the stomach or interaction with the immune system. The possible consequence of leakage of the vector into the environment is expected to be low as shedding is minimal and transient. Nevertheless, recombination with endogenous pathogenic replication-competent adenovirus might occur, therefore leading to AAV2/2 replication.

5.2.3 Summary of Benefits: Risks

The overall risk-benefit balance of IVT injection of GS010 for the treatment of vision loss due to the *ND4* mutation causing LHON is not yet available as no formal clinical efficacy analysis has been provided at the time of planning of this long-term follow-up study. The IMP, GS010, is considered to be safe and well tolerated.

5.3 Study Rationale

The dramatic loss of vision in individuals with LHON is life-changing, disabling, and affects their families socially, emotionally, and financially. LHON greatly alters a patient's ability to perform daily activities, reduces a patient's autonomy, and particularly disrupts the ability to read. The quality of life (QOL) in patients with LHON remains poor, even relative to other forms of chronic vision loss of other etiologies.¹⁶ LHON represents an urgent medical need.

Currently there is no approved therapeutic agent for the treatment of vision loss from LHON in the United States. The European Medicines Agency (EMA) provided conditional approval under exceptional circumstances for Raxone® (International Non-Proprietary Name [INN]: Idebenone) (Raxone® European Product Assessment Report 2015). A study of idebenone for the treatment of vision loss from LHON, caused by the three most common primary mutations (*ND1*, *ND4*, *ND6*), failed to reach its primary endpoint.¹⁷ Vision loss from LHON remains an unmet medical need.

The IMP, GS010, is a replication-defective single-stranded DNA recombinant adeno-associated virus 2 (rAAV2) vector containing a codon-modified complimentary DNA (cDNA), encoding the human wild type mitochondrial NADH dehydrogenase 4 protein (rAAV2/2-ND4), under the control of the cytomegalovirus immediate early promoter in an intron-containing expression cassette (beta globin intron, HBB2), flanked by the viral inverted terminal repeats from AAV2/2. GS010 is under development for the treatment of vision loss in LHON when due to the G11778A *ND4* mitochondrial mutation.

GS010 has received orphan drug status in both the United States of America (USA) and the European Union (EU) (respectively #13 4120 and #EMA/OD/164/10). GenSight Biologics has completed the preclinical development stage and has conducted a Phase I/II safety and tolerability trial. Subsequently, 2 Phase III clinical studies, the RESCUE and REVERSE studies (NCT02652767 and NCT02652780, respectively) of GS010, were initiated in the USA and EU. Subjects in the RESCUE and REVERSE were treated with the gene therapy IMP GS010 injected once in a single, randomly selected eye. The fellow eye received a sham IVT injection per the randomized treatment allocation. This long-term follow-up study will be considered part of the Phase III program and is an extension of the post-treatment 2-year

follow-up period.

Long-term Risk Assessment and Management

According to the EMA Committee for Medicinal Products for Human Use Guideline, entitled “Follow-Up of Patients Administered with Gene Therapy Medicinal Products,” and the United States Food and Drug Administration (US FDA) Center for Biologics Evaluation and Research Guidance for Industry (2006) entitled, “Gene Therapy Clinical Trials: Observing Subjects for Delayed Adverse Events,” viral vectors without integration, latency, or reactivation potential like AAV vectors present a low risk for gene therapy-related delayed adverse reactions. Although the FDA indicated that long-term follow-up is not considered necessary for this clinical development program, the EMA recommends a yearly monitoring plan up to 5 years post-treatment.

The regulatory intention of further observation is to determine the sustainability of efficacy, or whether declining efficacy after administration of gene therapy IMP occurs or whether more time is needed for tissue to be fully functional. For safety, the intention is to determine delayed-onset of adverse events (AEs), and to determine any additional unexplored long-term risks. The EMA refers to the Guideline (2008) entitled “Safety and Efficacy Follow-up: Risk Management of Advanced Therapy Medicinal Products” for possible delayed risks. One area for long-term observation is the potential risk directly related to the administration procedure of advanced therapies, and for this program would be the technique of IVT injection and any associated long-term effects.

In summary, all treated subjects in the RESCUE and REVERSE studies will be offered participation in the GS-LHON-CLIN06 study for the purpose of long-term safety evaluations, but only those providing informed consent and meeting eligibility criteria will be included in the study.

6. STUDY OBJECTIVES

6.1 Primary Study Objective

The primary objective of the study is:

To assess the long-term safety of intravitreal GS010 administration up to 5 years post-treatment in subjects who were treated in the RESCUE or REVERSE studies.

6.2 Secondary Study Objectives

The secondary objectives of the study are:

1. To assess the long-term efficacy of intravitreal GS010 administration up to 5 years post-treatment in subjects who were treated in the RESCUE or REVERSE studies.
2. To assess the QOL in subjects who were treated with intravitreal GS010 in the RESCUE or REVERSE studies for up to 5 years post-treatment.

7. INVESTIGATIONAL PLAN

7.1 Overall Study Design and Plan

This study will be a multinational multicenter prospective non-interventional long-term follow-up clinical study of subjects previously treated with GS010 in either the RESCUE or REVERSE studies. Of the 7 investigational centers participating, 4 are located in Europe (1 each in France, Germany, Italy, and the United Kingdom,) and 3 are located in the United States.

[figure not shown]
Subjects will be enrolled in the long-term follow-up study when informed consent is provided and inclusion/exclusion criteria are met. Enrollment will occur during the Inclusion Period, which will be during the RESCUE and REVERSE study Week 96/End-of-Study (EOS) Visit or anytime up to 1 day prior to the long-term follow-up study Visit 2 (Day 180). Preferably, the assessments required to be performed during the Inclusion Period will be conducted at the RESCUE and REVERSE study Week 96/EOS visit; however, if the subject cannot undergo all assessments at that time, the assessments may be performed at a later date during the Inclusion Period, but no later than one day before the Year 2.5 visit (Day 180).

The study population will be limited to the number of subjects treated in the RESCUE and REVERSE studies. The total length of the long-term follow-up study will be 3 years and the total length of the subject follow-up from IMP administration will be 5 years. The RESCUE and REVERSE long-term follow-up study is planned to start towards the end of 2017 and study start will be defined as the first subject's first visit in this study. The approximate study end date is planned to be towards the end of year 2022 after the last subject's last visit.

The follow-up will include onsite assessments of safety, QOL, and efficacy as in the RESCUE and REVERSE studies. The study will include 5 follow-up study visits: at 2.0-, 2.5-, 3-, 4-, and 5 years post-treatment.

Statistical analysis of the data will include descriptive summaries of safety, QOL assessments, and statistical testing of efficacy endpoints.

Figure 1: Study Design Schematic of the Long-term Follow-up of Subjects from the RESCUE and REVERSE Clinical Studies

Note: Inclusion into the long-term follow-up study will be allowed from W96 up to 1 day prior to Y2.5.

7.2 Study Endpoints

7.2.1 Primary Study Endpoint

The primary study endpoint is:

1. Adverse events (AEs) or serious adverse events (SAEs) (ocular or systemic) related to IMP or administration procedure, as judged by the Investigator, reported during the long-term follow-up visits (2, 2.5, 3, 4, and 5 years) from the period of 96 weeks up to 5 years post-treatment and summarized descriptively by type, frequency (number, percentage), severity, causal relationship, and seriousness.

7.2.2 Secondary Study Endpoints

The secondary study endpoints are:

1. Ocular or vision-related AEs reported during the post-treatment long-term follow-up visits from the period of 96 weeks up to 5 years and summarized descriptively by type, frequency (number, percentage), severity, causal relationship, and seriousness.
2. Change in contrast sensitivity measured with the Pelli-Robson chart in all-, best-, and worst-eyes treated with GS010 IVT injection compared to all-, best-, and worst-eyes treated with sham IVT injection respectively, from the RESCUE or REVERSE study baselines and pooled, to the follow-up study time points (2, 3, 4, and 5 years).
3. Change in best corrected visual acuity (BCVA) reported with Logarithm of the Minimal Angle of Resolution (LogMAR), change of parameters measured with Humphrey™ visual field (HVF) 30-2, and change of parameters measured with spectral-domain optical coherence tomography (SD-OCT) in all-, best- and worst-eyes treated with GS010 IVT injection compared to all-, best-, and worst-eyes treated with sham IVT injection respectively, from the RESCUE or REVERSE study baselines and

- pooled, to each follow-up study time points (2, 2.5, 3, 4, and 5 years).
4. Response status of eyes treated with GS010 IVT injection compared to eyes treated with sham IVT injection, including all-, best- and worst-eyes receiving GS010 or sham respectively, with responder eyes defined by:
 - a. An improvement of at least 15 ETDRS letters (equivalent to a decrease of at least 0.3 LogMAR) compared to baseline, or having a Snellen acuity equivalent better than 20/200. The McNemar test will be used for comparisons from the RESCUE or REVERSE study baselines and pooled, to each of the follow-up study time points (2, 2.5, 3, 4, and 5 years).
 - b. Eyes that lose less than the 15 ETDRS letters (equivalent to an increase of less than 0.3 LogMAR) compared to the RESCUE or REVERSE study baselines and pooled.
 5. Response status of subjects whose ETDRS scores of the treated eye are at least 15 letters better than the sham eye or whose treated eye has a LogMAR acuity of at least 0.3 LogMAR better than the sham eye at each long-term follow-up visit (2, 2.5, 3, 4, and 5 years) in the RESCUE and REVERSE studies and pooled.
 6. Time course of the response in eyes treated with GS010 IVT injection compared to eyes treated with sham IVT injection, for the BCVA reported with LogMAR, for parameters measured with HVF 30-2 and for parameters measured with SD-OCT, with comparisons from the RESCUE or REVERSE study baselines and pooled, to each follow-up study time point (2, 2.5, 3, 4, and 5 years) using mixed effects models with repeated measures (MMRM).
 7. Time course of the response in eyes treated with GS010 IVT injection compared to eyes treated with sham IVT injection, for contrast sensitivity measured with the Pelli-Robson chart with comparisons from the RESCUE or REVERSE study baselines and pooled, to follow-up study time points (2, 3, 4, and 5 years) using MMRM.
 8. Visual improvement as measured by LogMAR by analysis of covariance (ANCOVA) to determine the difference in improvement for all-GS010 eyes compared to all-sham eyes, for best-GS010 eyes compared to best-sham eyes and for worst-GS010 eyes compared to worst-sham eyes, with comparisons from the RESCUE or REVERSE study baselines and pooled, to each follow-up study time point (2, 2.5, 3, 4, and 5 years).
 9. Change of ganglion cell layer (GCL) thickness/volume and topographical map and other parameters measured by SD-OCT (e.g., retinal nerve fiber layer and quadrantal thickness analyses) for all-GS010 eyes compared to all-sham eyes, for best-GS010 eyes compared to best-sham eyes and for worst-GS010 eyes compared to worst-sham eyes, from the RESCUE or REVERSE study baselines and pooled, to each follow-up study time point (2, 2.5, 3, 4, and 5 years) using (MMRM).

10. QOL as measured with the Visual Functioning Questionnaire 25 (VFQ-25) and 36-Item Short Form Health Survey, version 2 (SF-36-v2) subject-rated instruments and summarized descriptively with within-group comparisons from the RESCUE or REVERSE study baselines and pooled, to each follow-up study time point (2, 2.5, 3, 4, and 5 years).

7.3 Study Population

The study population will include subjects who were treated with GS010 in either of the 2 Phase III trials—RESCUE and REVERSE. Subjects will have had vision loss and been diagnosed with LHON due to the G11778A point mutation in the mitochondrial *ND4* gene. Subjects will have received a single IVT injection of the gene therapy GS010 in a single randomly-selected eye in the RESCUE or REVERSE studies.

Subjects will provide informed consent and will be enrolled after all inclusion/exclusion criteria are met.

7.3.1 Inclusion Criteria

Subjects **MUST** satisfy all the following entry criteria before they will be allowed to participate in the study:

1. Subject was treated with GS010 IVT injection in either of the RESCUE or REVERSE Phase III clinical studies.
2. Subject of legal consent age has provided informed consent; subjects that are not of legal consent age have undergone their country-approved clinical trial enrollment consent process.

7.3.2 Exclusion Criteria

If any of the following apply, the subject **MUST NOT** enter the study:

1. Subject is unwilling or unable to comply with the protocol requirements.
2. Subject has any medical or psychological condition that, in the opinion of the Investigator, may compromise their safe participation in the study.
3. Subject is taking or intending to take idebenone during the long-term follow-up study period.

7.3.3 Subject Withdrawal/Early Subject Termination

In accordance with the Declaration of Helsinki and the applicable regulations, a subject has the right to withdraw from the study at any time and for any reason without prejudice to his or her future medical care by the physician or at the institution.

Subjects will be withdrawn from the study under any of the following circumstances:

- The subject's request, at any time and for any reason.
- The Investigator decides that the subject should be withdrawn and the study is not in the subject's best interest. The Sponsor or Sponsor designee is to be notified immediately.

- The Investigator, the Sponsor, or the Health Authority, for any reason, stops the study.
- The subject fails to return to the investigational site for scheduled visits and does not respond to telephone or written attempts at contact.
 - If the subject fails to attend the scheduled visit, there will be at least 2 attempts to contact the subject via telephone and 2 written communications. If these receive no reply the subject will be considered lost to follow-up.

Subjects who are lost to follow-up, who dropped out, or who were discontinued will not be replaced.

The reason for withdrawal will be recorded in the clinical records and the electronic case report form (eCRF). All subjects who are withdrawn from the study will undergo an Early Termination visit (ETV).

Evaluations at Withdrawal

For any subject who is withdrawn before completing all study visits, the Investigator should:

- Perform an ETV
- Complete all appropriate eCRF pages, providing the date of and explanation for the subject's withdrawal/discontinuation.

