8.2 Schedule of Events

The Schedule of Events (**Table 1**) provides the procedures/assessments to be performed at each scheduled visit for long-term follow-up period.

The inclusion assessments may be performed at the Week 96/EOS visit of RESCUE/REVERSE and up to 1 day prior to the Visit 2 (Year 2.5 visit [up to 180 days post Week 96]).

Table 1: Schedule of Events

Years post-treatment	Inclusion Period	Long-term Follow-up Period			
	Year 2 (Week 96) ^a	Year 2.5 (± 4 weeks)	Year 3 (± 4 weeks)	Year 4 (± 4 weeks)	Year 5 EOS (± 4 weeks) ^b
Procedure	Visit 1	Visit 2	Visit 3	Visit 4	Visit 5
Informed consent	X				
Clinical Assessments/Procedures					
Review inclusion/exclusion criteria	X				
Medical history	X				
Physical examination including vital signs ^c	X				X
Electrocardiogram (12-lead)	X				X
Review concomitant medications	X	X	X	X	X
Adverse events/serious adverse events ^d	X	X	X	X	X
Laboratory Assessments					
Hematology/serum chemistry including liver function ^e	X				X
Quality of Life Assessments					
VFQ-25 ^f	X		X	X	X
SF-36 ^f	X		X	X	X
Ocular and Vision Assessments					
Slit-lamp examination ^g	X	X	X	X	X
Goldmann applanation tonometry for intraocular pressure ^h	X	X	X	X	X
Refraction for BCVA	X	X	X	X	X
Visual Acuity (ETDRS)	X	X	X	X	X
Humphrey TM visual field 30-2	X	X	X	X	X
Pelli-Robson contrast sensitivity ^h	X		X	X	X
SD-OCT	X	X	X	X	X
Color fundus photography	X	X	X	X	X

Abbreviations: BCVA, best-corrected visual acuity; EOS, End of Study; ETDRS, Early Treatment Diabetic Retinopathy Study; SD-OCT, spectral domain optical coherence tomography; SF-36v2, 36-item Short Form Health Survey; VFQ-25, Visual Function Questionnaire-25, version 2.

^a The inclusion window will be from Week 96 visit up to 1 day prior to Visit 2, which will be approximately 180 days post W96/EOS.

^b Subjects who discontinue participation in the long-term follow-up study prematurely (i.e., prior to Visit 5) will complete an EOS visit, including Visit 5 procedures.

- ^c Examination includes general appearance, skin, head, eyes, ears, nose, throat, neck, thyroid, chest/lungs, heart, abdomen, lymph nodes, extremities, and body weight and height. Vital signs include temperature, pulse rate, and systolic and diastolic blood pressure.

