- Treatment that is elective or has been planned in advance for a pre-existing condition and non-exacerbating condition.

Serious Adverse Event Documentation and Reporting

Reporting requirements for SAEs will be managed on behalf of GenSight by a third-party vendor.

Any SAE occurring during the course of the study, i.e., between the ICF signature and the EOS visit, **MUST be reported** to the Sponsor or their representative as soon as it becomes known. The Investigator must complete and email or fax a "Serious Adverse Event Form" to the Sponsor or their designee within 24 hours of occurrence or knowledge of the event.

An Investigator's delegate may complete the SAE form; however, the Principal Investigator or delegate physician must sign it. The form can be sent to the Sponsor or their designee with the delegate's signature if the Principal Investigator/delegate physician's signature cannot be obtained within one working day. The Principal Investigator/delegate physician's signature must be obtained as soon as possible, as must his/her evaluation of the relationship to the IMP. The signed form must be emailed or faxed to the Sponsor or their designee immediately.

The SAE form must be completed in English.

The initial report should be promptly followed by detailed, written reports, which will include copies of hospital case reports, autopsy reports and other documents when requested and applicable.

The Sponsor or designee will assess initial and follow-up SAE reports from the site for expectedness, which will be determined based on the most recent edition of the Investigator's Brochure. Reports of Suspected Unexpected Serious Adverse Reactions will be expedited to the regulatory authorities as required per local regulations as an Investigational New Drug (IND) Safety Report within the required time frame.

The Sponsor or designee will be responsible for informing the institutional review board(s) (IRB)/independent ethics committee(s) (IEC) of SAEs as required. Correspondence with the IRB/IEC relating to the reporting of SAEs will be retained in the study file. The Investigator will receive a copy of all correspondence with the IRB/IEC and maintain in the site files.

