10.6 Procedures in Case of Pregnancy

If a subject or the partner of a male subject becomes pregnant during the study, the subject should inform the Investigator and provide a copy of the positive pregnancy test and estimated date of the pregnancy. Pregnancy in itself is not regarded as an AE unless there is a suspicion that the IMP may have interfered with the effectiveness of a contraceptive medication.

The outcome of all pregnancies (i.e., spontaneous miscarriage, elective termination, normal birth, or congenital abnormality) that begin before Visit 5 must be followed up and documented even if the subject was discontinued from the study. A pregnancy outcome of a congenital abnormality/birth defect or of a spontaneous miscarriage would qualify as an SAE and be reported to the Sponsor or designee for processing to the regulatory authorities. A pregnancy outcome of an elective abortion without evidence of complications would not be processed as an AE.

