8.6.1 Adverse Events

All adverse events analyses will be presented with number of patients with at least one AE and number of events.

Primary Safety Analysis

The primary safety variables are:

- Adverse events (AEs) or serious adverse events (SAEs) (ocular or systemic) related to IMP (=GS010=study drug) or administration procedure, as judged by the Investigator, reported during the long-term follow-up visits (2, 2.5, 3, 4, and 5 years) from the period of 96 weeks up to 5 years post-treatment and summarized descriptively by type, frequency (number, percentage), severity, causal relationship, and seriousness.

Adverse events and SAEs related to study drug or study procedure will be summarized in two different ways: (1) systemic AEs and SAEs related to study drug or procedure or both, and (2) ocular AEs and SAEs related to study drug or procedure or both. Systemic AE data will be summarized by all subjects. Ocular AE data will be summarized by sham eye only, GS010 eye only, and both eyes.

The following summaries will be produced for (1) SAEs unrelated to study drug or procedure or both, (2) systemic AEs/SAEs related to study drug or procedure or both, and (3) ocular AEs/SAEs related to study drug or procedure or both, using counts and percentage as follows:

- Overall summary of AEs/SAEs related to study drug or procedure or both
- AEs related to study drug or procedure or both, including the number of events reported
- AEs/SAEs related to study drug or procedure or both by maximum severity
- AEs/SAEs related to study drug or procedure or both leading to study discontinuation
- SAEs related to study drug or procedure or both
- SAEs related to study drug or procedure or both leading to death.

Note that AE summaries will be provided for AEs collected during the originating study (RESCUE or REVERSE studies), for the follow-up period of CLIN-06, and combined.

Events will be coded using the current version of MedDRA and summarized by system organ class (SOC) and preferred term (PT).

Secondary Safety Analysis

The secondary safety endpoints are:

- Ocular or vision-related adverse events reported during the post-treatment long-term follow-up visits from the period of 96 weeks up to 5 years and summarized descriptively by type, frequency (number, percentage), severity, causal relationship, and seriousness.

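### New-onset safety events are not collected after a subject leaves early, and the rules on loss to follow-up and on the end of SAE reporting make leaving early easier than a 5-year safety endpoint warrants

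*Protocol*

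**What the plan says.** **Loss to follow-up.** Protocol 7.3.3 lists the circumstances in which subjects will be withdrawn. One reads: "The subject fails to return to the investigational site for scheduled visits and does not respond to telephone or written attempts at contact". That sentence speaks of visits in the plural. The rule beneath it works on a single visit: "If the subject fails to attend the scheduled visit, there will be at least 2 attempts to contact the subject via telephone and 2 written" messages, and then "If these receive no reply the subject will be considered lost to follow-up". The section sets no deadline for these contacts and prescribes none at later visit windows. It also requires an early termination visit (ETV) for every withdrawn subject.

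**Early termination and SAE reporting.** Under Protocol Table 1, footnote b, subjects who discontinue before Visit 5 "will complete an EOS visit, including Visit 5 procedures". Protocol 10.2 defines the reporting period this way: "Any SAE occurring during the course of the study, i.e., between the ICF signature and the EOS visit".

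**What continues.** Protocol 10.4 requires proactive follow-up once an SAE has been reported. It also has related AEs that began before the final visit monitored to resolution or for 30 days, whichever comes first. Under Protocol 10.6, outcomes of pregnancies that begin before Visit 5 "must be followed up and documented even if the subject was discontinued from the study".

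**Analysis.** The Safety Population (Protocol 11.4.1, SAP 6.1) is everyone who was treated and consented to follow-up, however long they stayed. SAP 8.6.1 states: "All adverse events analyses will be presented with number of patients with at least one AE and number of events". Counts and percentages follow, and no exposure adjustment is described.

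**The concern.** Protocol 5.3 gives detection of delayed-onset events as the safety purpose of the study, and the primary endpoint (Protocol 7.2.1) runs to 5 years. A subject who leaves early contributes nothing on new events from then on, yet stays in the denominator. The unobserved years therefore count as event-free, and the shortfall is greatest for the latest events. The population is capped at those treated in RESCUE and REVERSE, and dropouts are not replaced, so the lost information cannot be made up elsewhere.

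The protocol already uses the tools that would limit the loss. Section 10.1.2 asks about health since the last visit and allows contact with the primary physician to complete AE details. Section 10.6 follows pregnancies after discontinuation. Neither approach is extended to new AEs or SAEs after withdrawal.

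**Working it through.** The plan states no dropout rate, enrolled number or expected event count, so there is no figure to reproduce. The check is a reading of the text followed by arithmetic on the visit schedule.

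**1. Two routes out of the study**

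- *Unreachable subjects (7.3.3).* The trigger is a missed visit plus at least 2 + 2 = 4 unanswered contacts. Whether one missed visit is enough depends on whether the singular or the plural wording governs. Observation ends because contact ends. An ETV cannot take place, so the requirement that all withdrawn subjects have one conflicts with this route.
- *Subjects who discontinue while in contact.* Footnote b makes their last visit an EOS visit, and 10.2 ends reporting at the EOS visit. Read together, these close reporting of new SAEs at the ETV. Against that, Protocol 9.2 to 9.4 name the ETV as an alternative to Visit 5/EOS, and 10.4 equates the final visit with Visit 5/EOS. The two readings must be reconciled.

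On either route, no section provides for telephone, record-based or vital-status collection of new events after withdrawal.

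**2. Follow-up lost per subject**

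Window = 5 × 365.25 − 96 × 7 = 1826 − 672 = 1154 days = 3.16 years. Time lost = 5 years minus the time of the last visit attended.

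| First visit missed | Last visit attended | Time lost | Share of window |
|---|---|---|---|
| Year 2.5 | Week 96 | 3.16 y | 100% |
| Year 3 | Year 2.5 | 2.5 y | 79% |
| Year 4 | Year 3 | 2.0 y | 63% |
| Year 5 | Year 4 | 1.0 y | 32% |

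**3. Follow-up lost overall (assumed dropout of 10-20%)**

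- *Departures uniform in time:* the average loss is half the window, so 0.5 × 10% = 5% and 0.5 × 20% = 10%.
- *Departures spread evenly over the four visits above:* the mean loss is (3.16 + 2.5 + 2.0 + 1.0)/4 = 2.17 y, or 68.5% of the window. This gives 6.9% at 10% dropout and 13.7% at 20%.

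The range is therefore about 5-14%.

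**4. Final year only**

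- *Uniform departures:* 789/1154 = 68.4% of dropouts leave before Year 4 and lose the whole year. The other 31.6% lose half of it on average. Then 0.684 + 0.158 = 0.842, and 0.842 × 10-20% = 8-17%.
- *Visit-based departures:* every dropout loses the whole final year, so 10-20%.

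**5. Effect on a crude percentage (visit-based departures, constant event rate)**

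Let p be the true incidence over the window, d the dropout proportion, and λ = −ln(1 − p)/3.16. Observed incidence = (1 − d)p + d × mean of [1 − exp(−λ(3.16 − time lost))] over the four rows. For p = 5% this gives 4.66% at d = 10% and 4.32% at d = 20%. The crude percentage captures about 93% and 86% of the true value, almost unchanged for p from 2% to 10%.

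**The case against.** Several stronger readings are tempting, and the documents do not support them.

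- *A single missed visit withdraws a subject.* It does not. At least four contacts must also go unanswered, the main withdrawal ground uses the plural, and nothing bars a site from trying again later. SAP 8.1 reports missed visits as well as withdrawals.
- *A subject who replies but cannot travel must be withdrawn.* Section 7.3.3 requires both non-attendance and non-response, so this subject can stay enrolled, with SAEs still reportable and AE enquiry at the next visit attended. What is missing is any prescribed remote enquiry in the meantime.
- *The ETV ends SAE collection.* No sentence says so. It is an inference from two sections that others make ambiguous, and it cannot apply to subjects who never attend an ETV.
- *Nothing is collected after withdrawal, apart from pregnancies.* Section 10.4 continues follow-up of events already identified. The gap is confined to new-onset events.
- *The loss is selective.* It is plausible that sicker or worse-seeing subjects leave first, but the documents give no evidence for it.

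It is also fair to say that the primary endpoint is descriptive with no formal inference (Protocol 11.3), and that SAP 8.1 discloses withdrawals, reasons and attendance. A reader can therefore see that follow-up was incomplete. Disclosure does not recover the events, however, and the AE percentages themselves are not adjusted. Finally, not all lost time is due to these rules: subjects who withdraw consent or stay unreachable would be lost under any wording.

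**Conclusion.** The point holds in a limited form. The protocol permits a subject to be declared lost after one unanswered missed visit without prescribing further attempts. It can be read as closing SAE reporting at an early ETV, and it collects no new-onset AEs or SAEs after withdrawal. The crude safety summaries then count the missing time as event-free.

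For an individual the loss is 32-100% of the window. Across the study it is about 5-14% of follow-up time, if dropout is 10-20% and departures are either uniform in time or spread evenly over visits. The dropout figures are assumptions, and the crude-percentage shortfall also assumes a constant event rate. Only the share from reachable, consenting subjects is recoverable, and the documents do not allow that share to be estimated. The change should be made because it is cheap and bears on the primary endpoint; the text does not show that the endpoint is invalid.

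**What to change.** **Protocol 7.3.3.** Reconcile the singular and plural wording. Record an unanswered missed visit as a missed visit, repeat the contact attempts at each remaining visit window, and declare loss to follow-up only after the Year 5 window closes. Require the ETV only where the subject can be reached.

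**Safety-only follow-up.** Offer subjects who stop on-site visits without withdrawing consent an AE/SAE enquiry, by telephone or through the primary physician, at each remaining nominal visit to Year 5.

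**Protocol 10.2 and Table 1 footnote b.** State that SAE reporting runs to Year 5 or withdrawal of consent, and that an early ETV does not end it.

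**Cost.** Protocol and consent wording, and a few calls by existing site staff. Events reported by telephone will be less detailed than those found at examination and should be flagged in the data and listings.
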